Once the tablets are completely set up, they will be shipped to the various sites and each site will be given the passcode to unlock the tablet. Research coordinators at each site will be responsible for the maintenance and usage of the tablets. Tablets should be restricted to areas of the hospital in which they will be used to recruit patients. It will be required that the tablets be kept in locked cabinets when not in use for the consent process. In order to prevent the loss of the tablets, the research coordinator at a given site should use a check-out sheet for research assistants and other personnel involved in this project to keep track of who has the tablet at any given time. As the tablets at other sites will be used solely for the purposes of consenting patients, they should remain in the hospital and should not be taken home by any individual for personal use. All tablets will also be given a location app so that stolen tablets can be found. All tablets will also have a label on them instructing that if found – whom to contact at both the local and national site.

The tablets will be set up with restrictions so that the ability to install other applications is disabled. While these restrictive settings can technically be undone by local study team members who know the Apple ID credentials, it will be the responsibility of the research coordinator at each site to monitor the use of the iPads and ensure that they are not used for purposes outside of this study.

Before and after each patient is consented, the tablet should be wiped down using disinfecting wipes in order to prevent the spread of bacteria among patients and staff.

If a tablet is lost or stolen, the research coordinator at the given site should immediately contact the research coordinator at Lurie Children's. At this point, plans will be arranged between the two sites to obtain a new tablet. All tablets will also be given a location app so that stolen tablets can be found. All tablets will also have a label on them instructing that if found – whom to contact at both the local and national site.

Interim monitoring:

The following scale will be used in grading severity of adverse events noted during the study:

Mild adverse event: An infection resulting in continued antibiotic use or a return visit to the Emergency Department. Normal healing without further intervention.

Moderate adverse event: An infection resulting in a return visit to the Emergency Department with the potential for functional difficulties. Return to operating room for debridement.

Severe: A necrotizing infection with the potential for functional difficulties. Multiple debridements necessary in the operating room.

Due to the presumed low infections rates (0-10%), all infection events will be identified and discussed. If any adverse events occur the research coordinator and/or PI at that site will be required to report the event to the PI at Lurie Children's. The PI will discuss any adverse events at bi-monthly phone conferences with the Executive Committee. Such cases will also be discussed amongst the Steering Committee and other site leaders during planned quarterly phone conferences. A formal review by the PI and Site Leaders will be made after the first 40 patients are recruited to see if the infection rate in the non-operative treatment group is above 10%.

If an infection is present, the Principle Investigator and Site Leaders from the various other locations, will discuss the case including the characteristics of the infection, bacteria found, implications of this infection, whether any deviation from the protocol may have been present.

Final analysis:

Statistical differences in the rate of infection and time to healing will be compared between the operatively and emergency room treated groups. Confidence intervals will be determined for the rate of infection, the time to healing and number of additional procedures needed. Kaplan-Meier curves will be created for comparison.

Termination policy:

If during the course of the study, the infection rate in the emergency room treated group is greater than 10% (after a minimum of 40 nonoperatively treated patients) the study will be terminated.

Organization

Participating Investigators:

The central study center will be Ann & Robert H. Lurie Children's Hospital of Chicago (Lurie Children's). It is there that the Principal Investigator and Study Coordinator will be located. The pilot study has taken place at this location. Four additional sites will be included in the Phase 2 of the study. Each of these sites will have a Site Leader (SL) and supported by in house study

personnel. The five sites will be utilized to insure that the recruitment operation, site randomization, and organizational procedures are in place. All data will be run through, housed and analyzed at Lurie Children's. Finally, eight to ten additional sites, (locations to be determined) will be recruited, for a total of 13 -15 sites, each with their own Site Leader to complete the recruitment and treatment of patients.

Study Administration:

Executive committee: This will be made up of the Primary Investigator, Site Leaders from the 5 sites indicated above, and one volunteer from an external site not directly enrolling in the study. They will be in charge reviewing protocol deviations, counseling on study issues, and noting complications. They will meet monthly.

Steering committee – This will be made up of the Primary Investigator and all Site Leaders. They will be in charge of overall organization and will determine if an unsatisfactory rate of infection (>10%) is found.

Funding organization – Funding for the study will be attempted after phase 2 has been completed through NIH and the Pediatric Orthopaedic Society of North America. Funding will be needed for study coordinators and administrative needs. Phase 3 funding will be attempted through NIH and the Orthopaedic Research Education Fund.

Ethical issues:

The main ethical issue associated with this research would be if there is an increased infection rate with children who are randomized to the non-operative arm. These children may require longer term antibiotics or additional surgery. However, if a single surgery is ultimately necessary, the patient may only have lost minor healing time since a surgery was saved initially. Due to the fact that there are now three case series reporting children treated nonoperatively for minor open fracture, multiple centers are using it as their standard treatment practice. While these retrospective studies do not demonstrate an increased infection rate, these case series were all underpowered to show a significant difference. In our survey to POSNA membership, 31% of respondents chose emergency room treatment while 69% chose an operative strategy in the treatment of type I open forearm fracture. Therefore, equipoise exists for this question. The main benefit of this study will be to future children with open fractures. The children in the study will benefit if they were randomized to the ED group and the data shows no signs of infection and a normal healing time because they will have avoided a trip to the operating room.

Risks to Participants:

Patients with Type I open fractures are generally at minimal risk of problems if treated appropriately. The fracture should be treated within 24 hours of the injury to avoid infection. Infections may be caused by bacteria that contaminate the wound at the time of injury. Infections are unusual with this injury and can occur whether the child is taken to surgery. Infection may result in slow healing of the fracture and chronic bone infection. All children with fractures may also experience injury to the nerves or arteries or excessive swelling which can cause injury to muscle tissue. Risks of anesthesia in the Emergency Department or operating room may include breathing problems but are very rare in a previously healthy person. Participants who undergo surgery will be told of the risks related to anesthesia and surgery at that time and will sign a separate, treatment consent for the surgery and anesthesia. Risks of fracture treatment may include alignment problems or poor bone healing. Unknown risks may be involved with this research study.

Benefits:

The main benefit will be to future children with open fractures. The children in this study may benefit if they are randomized to the non-operative group and show no signs of infection with normal healing time. They will have been saved a trip to the operating room.

Survey Portion:

The practices and opinions toward type 1 open fractures in children will have been surveyed at the POSNA 2012 meeting as well as through a web based system (<http://www.surveymonkey.com/>) that will be distributed to all active members of POSNA after approval by the Evidence Based Medicine Committee. Approximately 600 members will be at the 2012 POSNA meeting. Those who complete the survey at the meeting and turn in their response will be entered into a raffle drawing for a \$500 Apple gift certificate. The raffle will take place at the end of the meeting. The odds of winning are 1:600. Additional POSNA members will be captured through the web-based survey which will be available after the meeting distribution. There is no incentive and/or raffle drawing for those who participate in the web based survey option after the meeting.

The questions can be reviewed as part of the supplementary data section. We believe that practice patterns vary significantly and that there will be no consensus opinion toward the treatment of type 1 open fractures in the pediatric population. This survey will provide the documentation of equipoise necessary to apply for additional funding as during phase 3 of the trial.

Subjects: The target population for this project is the entire membership of POSNA.

Survey Instrument:

We have developed 21 close-ended questions to study the attitudes and practices of the target audience along with their demographic information. We have pre tested the questionnaire by asking colleagues (Pediatric orthopedic surgeons within our practice, orthopedic residents) for feedback regarding the survey instrument. The survey will be sent out as a POSNA attachment on three separate occasions in order to obtain the highest percentage of responses. There will also be a question identifying if respondents are interested in participating in this study during Phase 3.

Statistics and Power Analysis

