Of the thirteen patients who agreed to participate, six were randomized to emergency room treatment and seven were randomized to operating room treatment. One of the patients, randomized to operating room treatment fracture was NOT found to have an open fracture and

will be eliminated from final formal assessment beyond intent to treat analysis. Another patient who was randomized to the operating room chose not to undergo surgery and instead received ED treatment only. None of the twelve patients' fractures, enrolled in the study, were complicated by infection or delayed healing. There have been no differences in anesthesia/sedation related complications.

E. Methods:

Clinical Trial Portion

Design of the study: A prospective, randomized unblinded non-inferiority clinical trial of children with Type I open fractures to evaluate whether emergency room management and close follow up will not be inferior to formal operative irrigation and debridement in terms of infection rates and bone healing times. The baseline rate of infection with open fractures, treated operatively, is noted to be 0-10% in the literature. We will choose a baseline infection rate of 1%.

Study population:

Inclusion Criteria - Patients will be included if their age is between 3 and 14 years, if the fracture is amenable to treatment by closed reduction, a low energy injury (falls from less than 10 feet, bicycle accidents), wounds less than 1 cm in length and the bone not visualized through the skin.

Exclusion Criteria - Patients will be excluded if they do not meet inclusion criteria, if the fracture would typically require operative reduction and fixation, if their mechanism was high energy (struck by vehicle, motor vehicle accidents, fall from height greater than 10 feet), if there is gross contamination of the wound, or if the open injury involved the hands or feet (the current standard of care to treat open injuries involving hands or feet is only emergency room management).

Study Procedures:

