Patients will be recruited from the emergency department at the participating hospitals. All patients with open fractures (fractures associated with a skin wound) who present to emergency department will be assessed for inclusion. The initial assessment of open fracture will be identified by the emergency room physician who will discuss with the attending on call. The orthopaedic attending will determine if this child is amenable to non-operative treatment and would be considered for study inclusion.

All children will be given antibiotics (Ancef 25mg/kg up to 1gm, or clindamycin if allergic to first generation cephalosporin or penicillin) and if the inclusion criteria are met, will be offered to participate in the study by the orthopaedic surgeon or their delegate. If the patient refused study inclusion, they will then be treated per the attending treating physician recommendation.

If the patient agrees to participate he/she will be randomized. The randomization chart is saved in the REDCap database and functions to randomly assign a patient who is entered into the database into a treatment group, stratifying by site. The attending physician will be responsible for determining the randomization assignment by either (1) logging into the REDCap database to enter the patient and randomize them or (2) calling the research coordinator or his/her representative who will then log in to REDCap to randomize the patient. As a backup, the research coordinator will have the randomizations for each site in numbered, sealed envelopes. The study coordinator will be available 24 hours a day to provide the randomization assignment, the consent form (see consent process below), and answer questions prior to treatment arm assignment. Children in both arms of the study will receive emergency room irrigation with one liter of normal saline, realignment/reduction of the fracture, and casting. Conscious sedation will

usually be necessary for this to occur. Patients will be admitted and have up to 24 hours from the time of injury to make a final decision.

No difference in outcomes have been shown in patients with open fractures treated with operative debridement in less than 6 hours compared with those treated from 6 to 24 hours.(8) The surgical timing will be determined by the attending orthopaedic surgeon.

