Baseline assessment will include the child's age, mechanism of injury, bone fractured, wound side and location, state of skin injury, whether gross contamination is present, neurovascular status, comorbid conditions.

Additionally, if patients do not wish to be randomized to a treatment arm, they will still be presented with an option for study enrollment. They may take part in a prospective chart review in which the same data will be collected as those patients who were randomized. The data collected at both the baseline and follow-up will match the data collected from patients who randomized to a treatment arm. Patients will consult with their physician regarding treatment for their injury and decide which treatment method they prefer. They will then be consented by the study coordinator or an investigator who will describe the study and the data that will be gathered from their medical charts.

Intervention allocation:

The randomization assignment will be completed and accessible only by the study coordinator. The coordinator will have the assignments in numbered, sealed, radio opaque envelopes in sequential order by the study site. The envelopes will be made by an independent study assistant and determined by block allocation with a 1:1 ratio of operative room vs. emergency room management with permuted, mixed blocks of 4 and 6 created randomly. Randomization will be stratified by each center but by no other factors. The order of these permuted blocks will be determined by random number chart.

Experimental and Control Interventions:

Children will be randomized into two treatment arms – formal operative management (OR) and emergency department (ED) management. Children randomized to the OR arm will be taken to the OR within 24 hours for irrigation and debridement and appropriate bone management. Patients who randomize to non-operative treatment will only be given conscious sedation in the emergency department where the bone will be reduced and casted and the wound will be washed out with one liter of normal saline. All patients will be admitted for 24 hours of intravenous antibiotics post treatment and then sent home with 7 days of oral antibiotics.

Follow up visit description and schedule:

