Research coordinators at other sites will be asked to send a monthly log to the research coordinator at Lurie Children's recording their recruitment process. Information recorded on this log will include the total number of patients approached for recruitment, the number enrolled, their treatment randomizations and whether they were consented by study investigators in person or remotely. The number of patients who did not meet inclusion criteria or who declined enrollment, as well as their reasons for declining, will also be recorded. The research coordinator at Lurie Children's will be in touch with the research coordinator at each site to ensure this monthly log is accurately completed. The local research coordinator will be responsible for keeping a database of the consent information for all patients enrolled at their site (whether they were consented in person or remotely). In the event that a site does not have research staff, the

research coordinator at Lurie Children's will be in communication with the PI on a monthly basis and will complete this recruitment log for them.

Tablet Setup and Use:

Prior to being distributed among the sites, tablets will be set up with the applications necessary to the consent process. Instructions regarding the use of these applications will be given to each site. The tablet at each site will have the required consent documents saved and easily accessible within the SignNow application. Use of the FaceTime application will require the research coordinator (or another investigator) to create an Apple ID that can be used as the general login for that site. The number for the research coordinator at Lurie Children's will be pre-programmed into the tablet.

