If we are only able to recruit 150 patients, and the rates of infection in the OR and ED groups are nearly equal, we will consider halting the study and releasing the results. This will be decided by the Steering Committee in conjunction with the funding agency. Alternatively, the Steering Committee could decide to prolong the study to achieve increased numbers for the comparison.

Data management:

An initial hard copy survey of the initial data will be completed by the attending surgeon with the study coordinator's assistance. Data collected will include name, MRN, telephone number, age, injury mechanism, bone fractured, wound size (in cm), wound location, state of skin, neurovascular status, comorbid conditions, antibiotics given, tetanus status, surgical procedure description and anesthesia/sedation complications. At the 1-week follow up visit, a survey will be completed by the attending surgeon which will ask if fevers are/have been present, wound drainage through cast, skin and wound examination (erythema, drainage), whether additional antibiotics are necessary, and the reduction of the bone on radiographs. The survey completed by the treating orthopaedic surgeon at subsequent visits will also ask if fevers are presents, if pain has increased, wound drainage, if a second look at the wound was necessary, reduction of the fracture, and healing.

An online database has been created using REDCap technology. Name, MRN and telephone number will be recorded in site-specific Excel files. Non-identifying data will be recorded in REDCap. Information from the initial and follow up visits will be entered into the databases by the surgeon or his representative which will be password protected. Each patient will have a unique identifier. Randomization allocation can also be found through the REDCap site.

Data Analysis:

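### Printing centre-level block sizes of 4 and 6 in an unblinded protocol would let someone with a site's full history forecast up to about 45% of assignments at 75% confidence: a ceiling, and cheap to lower

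*Combined protocol and SAP*

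**What the plan says.** In E. Methods, the Intervention allocation section prescribes "block allocation with a 1:1 ratio of operative room vs. emergency room management", using "permuted, mixed blocks of 4 and 6 created randomly. Randomization will be stratified by each center but by no other factors". It adds: "The order of these permuted blocks will be determined by random number chart". These sentences describe how the sealed, opaque envelopes are made up. The same section says that assignments are accessible only to the study coordinator.

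The Design of the study paragraph calls this "A prospective, randomized unblinded non-inferiority clinical trial of children with Type I open fractures". Under Study Procedures, "The orthopaedic attending will determine if this child is amenable to non-operative treatment and would be considered for study inclusion". The same attending is responsible for obtaining the assignment, either by "logging into the REDCap database to enter the patient and randomize them" or by calling the coordinator. There the REDCap chart, stratified by site, is the main route and the envelopes are a backup. No block structure is given for the REDCap chart.

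On past assignments, the Data management section states: "Randomization allocation can also be found through the REDCap site". The Data Security section lets each site see the data of its own patients, and mentions accounts for site principal investigators and research coordinators.

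**The concern.** Sealed envelopes hide the list. They do not prevent inference from assignments already made, which are visible in an unblinded trial. With 1:1 blocks of 4 or 6 within each centre, each past assignment changes the odds of the next, and a reader of the protocol knows the sizes.

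The step exposed is the decision to offer the trial, which partly depends on the attending's judgement. If a child with a more worrying wound were less likely to be offered randomisation when the emergency department (ED) arm looked likely, higher-risk children would drain from that arm and the infection difference would shrink towards non-inferiority. A family that is not randomised can still choose a treatment and join the chart-review cohort, so the alternative is easy. At the assumed 1% rate, only 0.01 × 150 = 1.5 infections are expected in the operating room (OR) arm, so a few diverted children can matter.

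**Working it through.** **1. The plan's own figure.** The plan gives no figure for predictability. Its nearest number is the power behind 300 children: 0.9111 at 150 per arm, a 1% rate in both arms and a 4-point margin. Full binomial enumeration with the unpooled Wald 95% interval gives 0.9105, so it reproduces. Step 5 uses the same enumeration.

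**2. Inputs.** Block sizes, ratio and stratification come from Intervention allocation. The 14 yearly rates come from Site estimates (2 to 20, total 128). Assumed: sizes 4 and 6 equally likely, the REDCap list built the same way as the envelopes, and the forecaster knows the sizes but not which is in use.

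Scaling by 300/128 turns yearly rates of 2, 4, 5, 9, 12 and 20 into 5, 9, 12, 21, 28 and 47 children. With the listed numbers of sites: 3×5 + 3×9 + 12 + 21 + 3×28 + 3×47 = 300.

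**3. Formula.** Let (a, b) be the ED and OR places left in the current block, starting at (2,2) or (3,3) with weight ½ each. Then P(next is ED) = Σ w(a,b) × a/(a+b). The weights are updated by Bayes' rule after each assignment, and a finished block restarts the mixture. By hand, for a site's first children:

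- Child 1: 0.50.
- Child 2 (switch of arm): ½ × 2/3 + ½ × 3/5 = 0.633.
- Child 3, when the first two match (probability 1 − 0.633 = 0.367): the weight on size 4 is (½ × 1/3)/0.367 = 0.455, so the other arm has 0.455 × 1 + 0.545 × 3/4 = 0.864. Otherwise 0.50.
- Child 4, after a 2:1 split: the weight on size 4 is (1/6)/(1/6 + 0.15) = 0.526, so the arm used once has 0.526 × 1 + 0.474 × 2/3 = 0.842. After three alike (probability 0.05) it is certain.

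Over four children the share at 75% or more is (0 + 0 + 0.367 + 1)/4 = 0.342. Longer sites were enumerated exactly up to 15 children and simulated beyond that.

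**4. Results over the 14 sites, 300 children, full history.** At 75% or more: 45% (about 135 children). At two-thirds or more: 53%. Certain: about 6%. Best guess correct: 68%. The 75% share is 31% at a site of 5 children, 43% at 12, 45% at 21 and 48% at 36. Varying the proportion of size-4 blocks from 30% to 70% gives 42% to 45%.

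| Share of site history seen | Forecast at ≥75% | Certain | Best guess correct |
|---|---|---|---|
| 100% | 45% | 6% | 68% |
| 90% | 33% | 4% | 65% |
| 75% | 20% | 2% | 62% |
| 50% | 7% | 0.4% | 58% |
| 25% | 1% | 0% | 55% |

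**5. Illustration of bias.** Assumed, with no source in the documents: 30% of children carry three times the infection risk, and half of them are not enrolled when ED is at least 75% likely. Full history is also assumed. Such slots supply about 38% of ED children and 9% of OR children (using 7% for OR moves no figure below by more than 0.1 point).

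- Mean relative risk without selection: 0.7 + 0.3 × 3 = 1.6.
- In affected slots: (0.7 + 0.15 × 3)/0.85 = 1.353, a ratio of 1.353/1.6 = 0.846.
- True rates of 5% (ED) and 1% (OR) become 5% × (1 − 0.38 × 0.154) = 4.71% and 1% × (1 − 0.09 × 0.154) = 0.99%. The difference falls from 4.0 to 3.7 points.
- Chance of falsely concluding non-inferiority: Newcombe interval 1.9% to 2.5%; Wald interval 5.2% to 6.9%.
- With 25% to 100% withheld: difference 3.9 to 3.3 points, Newcombe 2.1% to 3.8%, Wald 5.9% to 10.3%.

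**6. Wider mix of 4, 6, 8 and 10, sizes known, full history.** At 21 children per site, forecasts at 75% or more are 26% (45% with 4 and 6), certain ones about 1% (6%), and correct guesses 66% (68%). Over the 14 sites the counts are about 76 against 135 of 300. Forecasts at two-thirds or more do not fall: 57% against 52% at 21 children per site.

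**The case against.** A reader might infer that the screening surgeon can in practice call the next arm for nearly half the children. The documents do not support that. It needs one person who knows the sizes, holds the complete ordered history and uses it optimally. Study Procedures speaks of an attending on call, so screening may rotate. Data Security mentions REDCap accounts only for principal investigators and research coordinators, although Study Procedures lets the attending log in. Nothing shows attendings following the sequence, and missing one assignment in ten already cuts the share to a third.

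A reader might also infer that the REDCap list certainly has this weakness. The sizes are written only for the envelopes; carrying them over is reasonable, since no other scheme is described, but it is an assumption. Nor does the lead coordinator's monthly recruitment log belong here: it concerns access to assignments, which that role already has, and block sizes do not change it.

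Other safeguards stand. Sizes are mixed at random, the eligibility criteria are explicit, all open fractures are to be assessed, and ineligible or declining patients are logged. These make selective offering partly visible but do not prevent it.

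The harm is also modest. The Newcombe error in the illustration rises only to the nominal 2.5%, and the Wald error exceeds 5% with no selection at all. With 75% of the history seen, the figures are 2.1% and 5.9%. What survives is narrower: concealment does not stop inference from past assignments, and the plan prints the information that makes inference easiest.

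**Conclusion.** The point holds as a cheap improvement, not as a defect that undermines the trial. If REDCap uses the envelope blocks and the full site history is known, up to about 45% of assignments could be forecast at 75% confidence. The realistic share depends on how much history an enrolling attending sees, which the documents do not tell us; 7% to 33% corresponds to seeing half to nine-tenths of it. The 75% threshold and the equal mix of sizes are choices made for this check.

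The direction of bias is plausible, but its size is illustrative only because the risk mix and withholding rate are assumed. On those assumptions it is small. The documents do not show that selective offering has occurred or that any attending predicts assignments.

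**What to change.** In Intervention allocation, replace *of 4 and 6* with: *randomly varying block sizes, recorded only in a restricted randomisation file not available to sites or to staff who enrol or consent*. State there and in Study Procedures that one scheme governs both REDCap and the backup envelopes, which also reconciles the two descriptions of how assignments are held. For assignments not yet issued, load a new table per centre with a wider random mix (for example 4, 6, 8 and 10), keeping 1:1 and stratification by centre.

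The gain should not be oversold. The wider mix reduces high-confidence forecasts but hardly moves the average guess rate, so withholding the sizes matters at least as much. Only children still to be randomised benefit: this version is dated 06/01/2015, and the project timeline has multicentre accrual running from January 2014 to August 2016.

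The cost is a short amendment and a new allocation table, with no extra patients or visits. Balance loosens slightly: the standard deviation of the difference in arm totals at 300 children goes from about 3.8 to about 4.8. This would be felt mostly at very small sites, since one expecting about 5 children may never complete a block of 8 or 10.
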